4.2.2. Main analytical approach

Primary analysis will be conducted using an inverse-probability weighted mixed model for repeated measures (MMRM) for the change from baseline in CAT score under the missing at random (MAR) assumption to handle missingness which may occur during the data collection.

The inverse probability weighting (IPW) method can reduce the selection bias caused by the missingness, by weighting the participants whose change from baseline of CAT score is observed at week 12 using the inverse probability of completeness in the endpoint. The key assumption for the IPW method is MAR which means that the missingness mechanism of the primary endpoint could be modelled using the observed factors, i.e. the baseline covariates and the post-baseline covariates by the time of missingness, and no unmeasured confounders are involved in the missingness mechanism.

To estimate the probability of the completeness of the primary endpoint, a logistic model is constructed to model its missingness mechanism with the missingness status as the dependent variable (status=observed, status=missing as the reference group). The following baseline and post-baseline covariates will be considered for the missingness of change from baseline in CAT score at week 12:

- Age,
- Gender,
- Years of COPD,
- Smoking history: smoking status and number of pack years,
- Pre-dose FEV1 at baseline,
- COPD maintenance treatment at baseline,
- CAT score at baseline,
- The change from baseline in CAT score at week 4,
- Intercurrent event status: no intercurrent events, received other COPD maintenance therapy, Trelegy discontinued due to other reason.
The subjects receiving other COPD maintenance therapy are those who have discontinued their Trelegy therapy and switched to other COPD maintenance therapy.
- Duration of Trelegy

The right tail of estimated weights may be truncated by its appropriate percentile if deemed necessary.

The change from baseline in CAT score will be analysed using the MMRM model with the covariates of smoking status, CAT score at baseline, visit, the interaction of CAT score at baseline*visit, in which each observation is weighted with the inverse probabilities derived from the above logistic regression models.

If a covariate is with missing values, the missing values in the covariate may be imputed if deemed necessary using appropriate imputation models with information by the time of its missingness. If any imputed covariate is used, the multiple imputation process will be employed to ensure the variability in the missingness of covariates are considered. At least 1000 datasets will be generated which include both observed and imputed values for the covariates. The inverse-probability weighted MMRM estimates, the corresponding standard errors and 95% confidence intervals from each dataset will be combined using the Rubin's rule.

Descriptive statistics will be summarized using the observed data.

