3.5.2. Concomitant Therapy

Any medication or vaccine for the treatment of a respiratory condition that the participant receives at the time of consent or receives during the study should be recorded along with:

- dates of administration including start and end dates
- dosage information including dose and frequency

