3.8.2 Statistical Analysis

3.8.2.1 Primary endpoint/estimand

Primary estimand

The primary clinical question of interest is: what is the change from baseline in CAT score at week 12, regardless of receiving a new COPD maintenance therapy or treatment discontinuation.

The estimand is described by the following attributes:

- Population: Symptomatic Chinese COPD participants who are receiving COPD maintenance treatment
- Treatment condition: Trelegy (FF/UME/CVI ELLIPTA 100/62.5/25 µg) one dose daily, inhaled
- Variable: change from baseline of CAT score at week 12.
- Intercurrent events:

- Receiving other COPD maintenance therapy is addressed by the treatment policy strategy.
- Treatment discontinuation due to any reason is addressed by the treatment policy strategy.
- Summary measure: average change from baseline in CAT score at week 12.

Rationale: Interest lies in the treatment effect at week 12 in the real-world setting, maybe confounded by other COPD maintenance therapies or the event of treatment discontinuation due to any reason. Therefore, treatment policy strategy is employed to handle the intercurrent events of receiving a new COPD maintenance therapy and treatment discontinuation due to any reason as it reflects the clinical practice.

Primary analysis

Primary analysis will be conducted using an inverse-probability weighted mixed model for repeated measures (MMRM) for the change from baseline in CAT score under the missing at random assumption to handle missingness which may occur during the data collection.

The missingness of the change from baseline in CAT score at week 12 will be modelled using a logistic regression model [Seaman SR and White IR, 2011], with the covariates of age, gender, years of COPD, smoker history, pre-dose FEV1 at baseline, COPD maintenance treatment at baseline, CAT score at baseline, the change from baseline in CAT score at week 4, intercurrent event status, duration of treatment exposure. The missingness of the change from baseline in CAT score at week 4 will be modelled analogously with the covariates collected before week 4.

The change from baseline in CAT score will be analysed using the MMRM model (in which each observation is weighted with the inverse probabilities derived from the above logistic regression models) with the covariates of smoking history, CAT score at baseline, visit, the interaction of CAT score at baseline*visit [Protocol No. CTT116855].

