4.2.3. Sensitivity analyses

Sensitivity analysis will be conducted using a MMRM with the covariates of smoking status, CAT score at baseline, visit, the interaction of CAT score at baseline*visit to derive the point estimate and the standard error of change from the baseline in the CAT score, but in which the

missing data in the primary endpoint will be imputed using monotone linear regression multiple imputation under missing at random assumption, for participants with no intercurrent events, receiving other COPD maintenance therapy, with treatment discontinuation, separately if data permits, otherwise may be imputed for the pooled groups, using the observed factors, i.e. the baseline covariates and the post-baseline covariates by the time of missingness.

The missing values in the covariate may be imputed with information by time of its missingness if deemed necessary.

At least 1000 datasets will be generated which include both observed and imputed values for the covariates. The MMRM estimates for the primary endpoint as well as the corresponding standard errors from each complete dataset will be combined using the Rubin's rule.

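### SAP 4.2.2 narrows the other-maintenance-therapy event to switchers, so participants who add a drug to Trelegy are coded event-free in the weighting and imputation models

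*SAP*

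**What the plan says.** - **Estimand.** Protocol 3.8.2.1 asks for the change in CAT at Week 12 "regardless of receiving a new COPD maintenance therapy or treatment discontinuation". It then lists two events, each with its own entry: "Receiving other COPD maintenance therapy is addressed by the treatment policy strategy" and "Treatment discontinuation due to any reason is addressed by the treatment policy strategy". SAP 4.2.1 repeats both. Neither document makes the first event depend on stopping Trelegy.
- **Coding for the primary analysis.** SAP 4.2.2 puts a three-level covariate into the logistic model for Week 12 missingness: "Intercurrent event status: no intercurrent events, received other COPD maintenance therapy, Trelegy discontinued due to other reason". The next sentence defines the middle level: "The subjects receiving other COPD maintenance therapy are those who have discontinued their Trelegy therapy and switched to other COPD maintenance therapy".
- **Second use of the grouping.** SAP 4.2.3 imputes "for participants with no intercurrent events, receiving other COPD maintenance therapy, with treatment discontinuation, separately if data permits", and otherwise for pooled groups.
- **Data collected.** Protocol 3.5.2 covers "Any medication or vaccine for the treatment of a respiratory condition that the participant receives at the time of consent or receives during the study", recorded with start and end dates and dosage. That section states no restriction on such use.
- **Declared changes.** SAP 4.8 lists only the move of the sensitivity analysis to an MMRM.

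**The concern.** The estimand and the variable that implements it do not match. Under SAP 4.2.2 the first event becomes a subset of the second (stopping Trelegy for any reason), so its separate entry in the estimand has no content of its own. Someone who stays on Trelegy and starts another maintenance drug has the first event as the estimand words it, but is event-free as the SAP codes it.

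The coding matters because SAP 4.2.2 rests the weighting on missingness being explained by observed factors. Add-on use is observed, but this covariate discards it. Duration of Trelegy cannot recover it, because these participants are still on Trelegy. Week 4 CAT change may pick up part of it, but not use that begins after Week 4. Protocol Table 3 plans for very different missingness in the two groups (5% against 30%, or 10% against 50%), so the choice of group is not neutral in principle. SAP 4.3.1 also reuses the primary weights for the CAT responder proportion.

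The documents alternate between *other* and *new* maintenance therapy. Every participant enters on a maintenance regimen (inclusion criterion 4), so the status of a prior inhaler that is simply continued is also undefined.

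**Working it through.** **1. Coding by elimination.**

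| Participant | Event in the estimand wording | Level in SAP 4.2.2 |
|---|---|---|
| Stays on Trelegy, nothing else | none | event-free |
| Stops Trelegy, switches to another maintenance drug | both | other therapy |
| Stops Trelegy, no switch | discontinuation | discontinued, other reason |
| Stays on Trelegy, starts another maintenance drug | other therapy | event-free (only level left) |

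The SAP does not state the last row in words; it follows from the three levels and the definition.

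**2. The plan's own figures.** Inputs from Protocol Tables 2 and 3: shares 0.79 / 0.20 / 0.01; means -2 / -2 / 0; SD 7; N = 460; overall mean -1.98.

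Half-width = 1.96 × sqrt( Σ [share/(1 − missing)] × [7² + (group mean + 1.98)²] / 460 )

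- Scenario 1: 1.96 × sqrt(49.04/460) = 0.640 (stated 0.64)
- Scenario 2: 1.96 × sqrt(55.81/460) = 0.683 (stated 0.69)
- Scenario 3: 1.96 × sqrt(64.38/460) = 0.733 (stated 0.73)

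These agree to within 0.01, so the planning arithmetic is not at issue.

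**3. Shift from coding add-on users as event-free.** The documents give no add-on frequency, so these inputs are assumed: a share *a* of the cohort, inside the 0.79 coded event-free, adds therapy; their mean change is *d*; their completeness is r1, against r0 for the rest. The other covariates are taken to absorb nothing. Weighting by status then reproduces the observed-case mean of the mixed group.

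- True group mean = [(0.79 − a)(−2) + a·d] / 0.79
- Weighted group mean = [(0.79 − a)·r0·(−2) + a·r1·d] / [(0.79 − a)·r0 + a·r1]
- Shift = 0.79 × (weighted − true)

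With d = −2, as in Table 2 for both groups, both means are −2 and the **shift is 0** at any *a*, r0 and r1.

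With d = 0 (the value Table 2 gives discontinuers, borrowed here) and Table 3's completeness for event-free and other-therapy participants:

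| a | r0, r1 | True | Weighted | Shift |
|---|---|---|---|---|
| 0.10 | 0.95, 0.70 | −1.38/0.79 = −1.747 | −1.311/0.7255 = −1.807 | −0.048 |
| 0.10 | 0.90, 0.50 | −1.747 | −1.242/0.671 = −1.851 | −0.082 |
| 0.20 | 0.95, 0.70 | −1.18/0.79 = −1.494 | −1.121/0.7005 = −1.600 | −0.084 |
| 0.20 | 0.90, 0.50 | −1.494 | −1.062/0.631 = −1.683 | −0.150 |

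**4. Keeping the planned 20%.** Step 3 adds these users to the planned 20%, giving 30-40% on other therapy in all. If they are instead part of the 20%, the mixed group is 0.79 + a. With d = 0, half of the 20% gives −0.048 (Scenario 2) and −0.083 (Scenario 3); all of it gives −0.089 and −0.156. With d = −1 each is about half as large. The half-width stays at 0.68 in Scenario 2 and 0.71 to 0.73 in Scenario 3.

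**5. Sign.** Take a = 0.10, d = 0, r0 = 0.95, but let add-on users never be missing (r1 = 1, assumed). The weighted mean is −1.311/0.7555 = −1.735, and the shift is 0.79 × (−1.735 + 1.747) = +0.009. The direction reverses.

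**The case against.** **The estimand is not altered.** A reader might infer that the SAP estimates something other than the protocol's target. It does not. Both events use treatment policy, so an add-on user's Week 12 score is kept and averaged whichever level is assigned. Population, variable, strategies and summary measure are unchanged. This stands.

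**Switching may be what the sponsor meant.** The protocol never defines other or new maintenance therapy. Its planning split of 79/20/1% is introduced with a 19% rate of withdrawal from Trelegy and treats the groups as exclusive, which fits a switch reading. This is a fair account of intent, but the estimand text in both documents does not say it, and SAP 4.8 is silent.

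**Add-on use is not hidden.** A reader might infer that it goes unreported, or that a published event-free share will be inflated. SAP 6.1.4 tabulates on-treatment COPD medications, and SAP 6.2.1 defines that period as first to last Trelegy date. No event-free share is a planned output, and the treatment-switch count in SAP 6.1.5 is right for switches. What remains is narrower: no planned output counts add-on use as an intercurrent event.

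**The size is assumed.** The add-on rate, the mean of 0 and the missingness are all assumptions, and the model also contains baseline CAT, FEV1, baseline treatment and Week 4 change. A reader might infer a bias that always favours Trelegy. That needs add-on users both to do worse and to be missing more often, and the documents establish neither.

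On the imputation groups, the link is by identical group names. SAP 4.2.3 does not restate the definition and allows pooling.

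**Conclusion.** The mismatch holds on the text: SAP 4.2.2 attaches a condition to the first intercurrent event that the estimand in Protocol 3.8.2.1 and SAP 4.2.1 does not contain, and SAP 4.8 does not declare it. Its reach is limited to the weights, the imputation groups and any count of events taken from this variable.

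The numerical effect is zero under Table 2's equal means. It is about −0.05 to −0.15 CAT units if 10-20% of participants add therapy, have mean change 0, have Table 3's other-therapy missingness, and nothing else in the model compensates. That is small beside a half-width of 0.64 to 0.73, in a study with no hypothesis test (SAP 2). The case for acting is that the definition and its implementation should agree in the primary analysis and that the correction is cheap, not that the result is likely to be materially biased.

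**What to change.** In SAP 4.2.2, give the status covariate a separate category for a new COPD maintenance therapy taken while Trelegy continues. Derive it from the medication dates already recorded under Protocol 3.5.2, and pool it with switchers if cells are small. State how a continued prior inhaler is classified. Counting any non-Trelegy maintenance dose after the first Trelegy dose would be too broad, since the clinical question speaks of a new therapy and a single leftover dose would qualify. Use the same categories in SAP 4.2.3 and add the count to SAP 6.1.5.

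Alternatively, if only switching was meant, say so in the estimand in both documents and list the definition in SAP 4.8.

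The first route costs a sentence or two of SAP wording, one derivation, one table row and one more covariate level, which may be sparse. It needs no new data.

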3.7.2 Sample size consideration

A sample size of 460 is planned. With the aforementioned assumptions in [Table 1](#), the sample size would be able to provide a half-width ranging from 0.64 to 0.73 for the 95% confidence interval (CI) of the inverse probability weighted mean of the change from baseline in CAT score at week 12 in the primary analysis under different missingness scenarios ([Table 3](#)).

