3.7.3 Sensitivity assessments

The half-width of confidence interval are assessed when the sample size varies under different missingness scenarios ([Table 3](#)). Scenario 1 is the ideal situation where no missingness occurs, which results a half-width of 0.64 for the 95% confidence interval for the inverse probability weighted mean of the primary endpoint with the sample size of 460. Scenario 2 represents a situation with the moderate missingness, which results a

half-width of 0.69 for the 95% confidence interval of the primary endpoint with the sample size of 460. Scenario 3 represents the worst missingness situation, which results a half-width of 0.73 for the 95% confidence interval of the primary endpoint with the sample size of 460.

Table 3 Sample size versus the half-width of the 95% CI for the primary endpoint

Sample size	Data availability status	Proportion of missing data at week 12			Expected inverse probability weighted mean	Half width of 95% CI
		Participants with no intercurrent events	Participants receiving other COPD maintenance therapy	Participants with treatment discontinuation		
280	Scenario 1	No missing	No missing	No missing	-1.98	0.82
	Scenario 2	5% missing	30% missing	50% missing	-1.98	0.87
	Scenario 3	10% missing	50% missing	70% missing	-1.98	0.94
340	Scenario 1	No missing	No missing	No missing	-1.98	0.74
	Scenario 2	5% missing	30% missing	50% missing	-1.98	0.79
	Scenario 3	10% missing	50% missing	70% missing	-1.98	0.85
400	Scenario 1	No missing	No missing	No missing	-1.98	0.69
	Scenario 2	5% missing	30% missing	50% missing	-1.98	0.73
	Scenario 3	10% missing	50% missing	70% missing	-1.98	0.78
460	Scenario 1	No missing	No missing	No missing	-1.98	0.64
	Scenario 2	5% missing	30% missing	50% missing	-1.98	0.69
	Scenario 3	10% missing	50% missing	70% missing	-1.98	0.73

With the planned sample size of 460, the half-width of the 95% confidence interval for the inverse probability weighted mean for the primary endpoint is also assessed when the standard deviation varies (Table 4).

Table 4 The half-width of the 95% CI versus standard deviations when N=460

Standard deviation	Data availability status	Proportion of missing data at week 12			Expected inverse probability weighted mean	Half width of 95% CI
		Participants with no intercurrent events	Participants receiving other COPD maintenance therapy	Participants with treatment discontinuation		
6.5	Scenario 1	No missing	No missing	No missing	-1.98	0.60

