4.3. Secondary Endpoints Analyses

4.3.1. Secondary endpoints

The analysis approach for the below secondary endpoints is analogous to the primary analysis and the sensitivity analyses for the primary endpoint:

- Change from baseline of Modified Medical Research Council (mMRC) at week 12
- Change from baseline of pre-dose FEV₁ at week 12
- Proportion of CAT responder (defined as ≥ 2 unit decrease from baseline) at week 12
- Change from baseline of CAT score at week 4

In the analysis for the proportion of CAT responder (defined as ≥ 2 unit decrease from baseline) at week 12, the considerations follow:

- Summary measure is the proportion of participants having ≥ 2 unit decrease from baseline at week 12.
- The response status of a participant at a visit is set to missing if his/her CAT score at baseline or at the visit is missing.
- The IPW weights used for primary endpoint were applied here to estimate the proportion of CAT responder at Week 12.

The missingness of the change from baseline in CAT score at week 4 will be modelled analogously as the primary analysis but with the covariates collected before week 4. The missing values in the covariates may be imputed with information by time of its missingness. The IPW weights are applied at the observation level, thus the observations for a same subject with available change from baseline in CAT score values at the week 4 and week 12 may have different weights.

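### As an ordinary correlated-residual MMRM, the weighted primary analysis adjusts twice for dropout related to Week 4 CAT change, which biases the Week 12 estimate even under MAR with correct weights

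*SAP*

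**What the plan says.** SAP 4.2.2 states: "Primary analysis will be conducted using an inverse-probability weighted mixed model for repeated measures (MMRM) for the change from baseline in CAT score". Protocol 3.8.2.1 specifies the same "inverse-probability weighted mixed model for repeated measures (MMRM) for the change from baseline in CAT score".

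The weights come from logistic models for whether CAT change is observed. The list of predictors for Week 12 missingness includes "The change from baseline in CAT score at week 4". The MMRM has smoking status, baseline CAT, visit and the baseline-CAT-by-visit interaction as covariates, so Week 4 and Week 12 changes are fitted jointly, "in which each observation is weighted with the inverse probabilities derived from the above logistic regression models". SAP 4.3.1 adds: "The IPW weights are applied at the observation level". One participant's two rows may therefore carry different weights.

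Neither document gives a within-participant covariance structure, says how the weights enter the likelihood, or names a robust variance estimator.

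The sensitivity analysis in SAP 4.2.3 is an MMRM in which "missing data in the primary endpoint will be imputed using monotone linear regression multiple imputation under missing at random assumption". It mentions no weights.

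**The concern.** An MMRM with correlated residuals already uses Week 4 data to adjust the Week 12 mean for people who drop out. If those with a poor Week 4 change leave, the covariance shifts the Week 12 mean accordingly. Weights built from the same Week 4 value shift it too. Applying both over-corrects.

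MAR does not remove the problem, and neither does a correctly specified missingness model. It also arises whether or not the two rows of a participant carry different weights. The estimate understates improvement if poor responders leave and overstates it if good responders leave.

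SAP 2 plans no hypothesis test, so the Week 12 estimate and its 95% interval are the primary result, and Protocol 3.8.3 says the study is meant to support licence renewal. Only CAT is affected: mMRC and spirometry have a single scheduled post-baseline visit.

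**Working it through.** **1. The plan's own precision figure.** Inputs from Protocol 3.7 (Tables 2 and 3): group shares 79%, 20% and 1%; SD 7.003; N=460; missing 5/30/50% by group in Scenario 2 and 10/50/70% in Scenario 3.

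Half-width = 1.96 × 7.003 × √(Σ p/(1−m) / 460)

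- Scenario 1: Σ = 1, giving 0.640.
- Scenario 2: Σ = 0.79/0.95 + 0.20/0.70 + 0.01/0.50 = 1.137, giving 0.682 (protocol 0.69).
- Scenario 3: Σ = 0.79/0.90 + 0.20/0.50 + 0.01/0.30 = 1.311, giving 0.733.

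This reproduces "a half-width ranging from 0.64 to 0.73 for the 95% confidence interval" at both ends. The formula is that of an inverse-probability weighted mean and contains no cross-visit correlation.

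Overall missingness is 0.79×0.05 + 0.20×0.30 + 0.01×0.50 = 10.45% in Scenario 2 and 0.79×0.10 + 0.20×0.50 + 0.01×0.70 = 18.6% in Scenario 3.

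**2. Algebra.** Let π be the probability that Week 12 is observed, Y1 and Y2 the Week 4 and Week 12 changes with means m1 and m2, and b the slope of Y2 on Y1. Take the usual weighted mixed-model form V = W^(−1/2) R W^(−1/2). A completer's Week 12 score is then proportional to

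w2 × [(Y2 − m2) − b √(w1/w2) (Y1 − m1)].

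With w1 = 1 and w2 = 1/π, its expectation is (E[Y2] − m2) − b E[√π (Y1 − m1)]. To first order,

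bias = −b × Cov(√π, Y1).

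This is zero only if b = 0 or if dropout is unrelated to Week 4 change. If worse (higher) Week 4 change lowers π, the bias is positive, so improvement is understated.

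**3. Large-sample check.** Two visits, SD 7, correct weights, unstructured covariance, maximum likelihood, Week 4 complete, n=400,000 (simulation error about 7/√400,000 = 0.011). The correlation of 0.6 and the odds ratios (OR, per SD of Week 4 change) are assumptions. Entries are bias in CAT points.

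| Missing | OR | Complete case | Weighted mean only | Unweighted MMRM | Weighted MMRM | Formula above |
|---|---|---|---|---|---|---|
| 10.5% | 1.5 | −0.167 | 0.010 | 0.007 | 0.097 | 0.084 |
| 10.5% | 2 | −0.291 | 0.002 | −0.003 | 0.152 | 0.141 |
| 18.6% | 1.5 | −0.311 | −0.001 | −0.001 | 0.159 | 0.141 |
| 18.6% | 2 | −0.492 | 0.012 | 0.008 | 0.279 | 0.235 |

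The overshoot is 51% to 58% of the complete-case bias in these rows (for example 0.279/0.492 = 57%). At OR 1 the bias is zero within simulation error.

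Variants at OR 1.5 to 2 and correlation 0.5 to 0.7:
- correct weights, n=1,000,000: +0.08 to +0.32;
- the same weight on both rows: +0.12 to +0.40;
- weights truncated at the 95th percentile: +0.07 to +0.25;
- Week 4 also 5% missing and weighted, with 18.6% missing at Week 12: +0.09 to +0.23.

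**4. At N=460.** 3,000 runs per cell; baseline CAT and its interaction with visit in the model; weights estimated from baseline CAT and Week 4 change; correlation 0.5 to 0.7; both missingness levels.

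| Analysis | Bias | 95% CI coverage |
|---|---|---|
| Weighted MMRM, OR 1.5 | +0.06 to +0.19 | 89.8–93.5% |
| Weighted MMRM, OR 2 | +0.12 to +0.29 | 83.4–92.2% |
| Same weights, independence covariance, sandwich SE | 0.015 or less in absolute value | 94.3–95.4% |

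If good responders leave at OR 2, the weighted MMRM bias is −0.12 to −0.29. The largest value, 0.29, is 0.29/0.73 = 40% of the Scenario 3 half-width.

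**5. Protocol scenarios as written.** With missingness set by intercurrent-event group and Table 2 means, the bias is about 0.01. If switchers are assumed 1 to 3 points worse at both visits, it is +0.02 to +0.14, and the unweighted MMRM is itself biased by −0.02 to −0.13.

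**The case against.** The strongest reply is that the plan is under-specified rather than wrong. It never states a correlated covariance; with independence the bias vanishes, and a weighted GEE using the full two-visit covariance is also unbiased (0.005 at 18.6% missing, OR 2, correlation 0.6). This is true, and it is why the finding is conditional. But correlated residuals are what MMRM ordinarily means, and nothing in either document rules them out.

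Second, the odds ratios and correlations are in neither document, and the bias is about 0.01 under Table 3 as written. This stands as a limit on size. However, Table 2 gives switchers the same mean as participants without intercurrent events, so those scenarios cannot reveal the problem, and the SAP treats dependence on Week 4 change as possible by listing it as a predictor. The upper figures use 18.6% missing, of which Protocol 3.7.3 says "Scenario 3 represents the worst missingness situation". Follow-up after stopping Trelegy (Protocol 3.2.1) and mapping of later early-discontinuation values to Week 12 (SAP 6.3.2) should keep missingness down.

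Third, bias does not explain all of the coverage loss. A bias of 0.29 with a correct SE of 0.363 gives Φ(1.96 − 0.80) − Φ(−1.96 − 0.80) = 87.4%, not 83.4%, so part is due to the SE. It is the smaller part: in a comparable cell (bias +0.30), replacing the model SE by a sandwich SE moved coverage only from 84% to 85.5%.

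Fourth, the adjustment is not fully doubled. In the usual weighting form the excess is roughly half of the complete-case bias. It comes close to a full second correction (+0.41 at 18.6% missing, OR 2, correlation 0.6) only if weights multiply the inverse covariance of the observed visits.

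Finally, the multiple-imputation sensitivity analysis does not share the fault and might show a discrepancy, but it would not correct the primary result.

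**Conclusion.** The concern holds, conditional on correlated residuals and on dropout that depends on the Week 4 residual. Under those two conditions the primary estimator is biased by construction, even when the plan's MAR assumption and missingness model are both right.

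The size is moderate: 0.06 to 0.29 CAT points at N=460 for the assumed odds ratios and correlations, against an assumed mean change of −1.98. The bias stays below half the planned half-width but is enough to pull interval coverage below 95%. The calculations simplify the ten-predictor missingness model to one or two drivers, so the figures show scale and are not a forecast. The change should be made because the flaw sits in the primary estimate and is cheap to avoid; it does not call the study design into question.

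**What to change.** In SAP 4.2.2, state that the weighted model is fitted with an independence working covariance, with participant-clustered sandwich or bootstrap standard errors, combined by Rubin's rule where covariates are imputed. This is in effect a weighted regression at each visit, apart from the smoking-status coefficient that the visits share. It also brings the analysis into line with the weighted mean on which the study was sized. A full-covariance weighted GEE would be an acceptable alternative if its form is written out.

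Keep the weights. Dropping them is not equivalent, because missingness predictors such as intercurrent-event status and duration of Trelegy are not in the MMRM mean model. The unweighted MMRM looks unbiased in step 3 only because Week 4 change is the sole driver of dropout there. The multiple-imputation MMRM in SAP 4.2.3 can stay as the sensitivity analysis.

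The cost is one sentence and one modelling option, with no new data. The possible price is a little cross-visit efficiency. None was lost at N=460: the empirical SE was 0.330 to 0.356 with independence and 0.333 to 0.363 with the correlated weighted MMRM, and independence was no worse in any cell.
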